9.2 Sample size determination

The primary objective of the study is to determine the superiority of dapagliflozin versus placebo added to standard of care in reducing the composite of CV death and heart failure events (hospitalisation for HF or urgent HF visit). Two hypotheses will be tested simultaneously (i.e., dual primary analyses) for the primary objective: (1) in the full population and in (2) an LVEF <60% subpopulation, with alpha allocated to each test. Originally, assuming a true hazard ratio (HR) of 0.80 between dapagliflozin and placebo, using a two-sided alpha of 5%, 844 primary endpoint

events were targeted in order to provide a statistical power of 90% for the test of the primary composite endpoint. To allow testing for the dual primary analyses, alpha will be allocated to each test to ensure strong control of the overall type I error rate. The target number of patients with a primary endpoint has been increased to 1117 in order to provide adequate statistical power for each test. It is anticipated that at least 70% of the events (i.e., approximately 780 events) will be available for the LVEF <60% subpopulation. To illustrate, assuming a true HR of 0.80, a two-sided alpha of 2.4% allocated to the LVEF <60% subpopulation will result in a power of 80% to detect a treatment difference, whereas an alpha allocation of 1.5% to the full population will result in 90% power. The final alpha split for the dual primary analyses will be specified in the SAP prior to the planned interim analysis. This is based on an overall 1:1 allocation between dapagliflozin and placebo.

The HR 0.80 was originally chosen as a conservative assumption based on the observed HR 0.72 (95% confidence interval 0.50-1.04) for the composite of HF hospitalisation and CV death in patients with HF at baseline in the EMPA-REG OUTCOME trial ([Fitchett et al 2016](#)) and HR 0.61 (0.46-0.80) for patients with history of HF in the CANVAS program ([Rådholm et al 2018](#)) considering that these were post-hoc analyses in subgroups with limited documentation of baseline HF diagnosis, not characterised by ejection fraction.

The event rate assumptions are based on sub analyses of the TOPCAT and I-PRESERVE studies by geographic region, NT-proBNP levels, prior hospitalisation for HF, and T2D status ([Pfeffer et al 2015](#), [Kristensen et al 2015](#), [Kristensen et al 2017](#)). The original sample size calculation (~ 4700 randomized patients) built on the assumption of an annual event rate of 9% in the placebo group for the majority of prevalent HFpEF patients, importantly all with NT -proBNP ≥ 300 pg/ml by inclusion criterion. Additionally, a subgroup of patients due to be discharged or recently discharged from a HF hospitalisation (here denoted ‘subacute’ patients) with a higher event rate is planned to be included. Assuming 20% of patients from the subacute category with an annual event rate of 24% during the first year and 9% thereafter for the remainder of the study, the original sample size of 4700 patients was estimated to provide the required number of 844 patients with a primary event during a recruitment period of 18 months and a minimum follow-up period of 15 months.

Based on the ongoing blinded monitoring of event accrual (including the percentage of patients from the subacute category), the sample size is increased from original 4700 to approximately 6100 randomised patients. Accordingly, the recruitment period is anticipated to increase from the original 18 months to 26 months. Recruitment might be marginally prolonged in a few countries to meet local targets. The study is event driven and the number of patients or duration may further change.

With the same event rate assumptions as above, assuming 11% of patients from the subacute category, approximately 6100 patients are estimated to provide the required number of 1117 patients with a primary event during an anticipated recruitment period of 26 months and a minimum follow-up period of 13.5 months (total study duration 39 months).

In addition, the expected number of patients who will be lost to follow-up is expected to be small; hence, these are not considered in the determination of the sample size.

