This study is event-driven with a target of 1117 patients with a primary endpoint event. The primary objective of the study is to determine the superiority of dapagliflozin versus placebo, when added to standard of care, in reducing the composite of CV death and HF events (hospitalisation for HF or urgent HF visit). Two hypotheses will be tested simultaneously (i.e, dual primary analyses) for this primary objective: (1) in the full population and in (2) an LVEF <60% subpopulation, with alpha allocated to each test. The final alpha split will be defined in the SAP prior to the interim analysis. It is anticipated that at least 70% of the events (i.e. approximately 780 events) will be available for the LVEF <60% subpopulation. To illustrate, assuming a true hazard ratio (HR) of 0.80 between dapagliflozin and placebo, a two-sided alpha of 1.5% would yield a power of 90% for the full population and a two-sided alpha of 2.4% would yield a power of 80% for the LVEF <60% subpopulation.

Based on above assumption and ongoing blinded monitoring of events accrual, approximately 6100 patients are estimated to provide the required number of primary events in the full population during an anticipated recruitment period up to 29 months and followed until the pre-specified number of primary events has occurred. Randomisation will be stratified by presence or absence of Type 2 Diabetes (T2D).

All patients who have been randomised to study treatment will be included in the Full Analysis Set (FAS) irrespective of their protocol adherence and continued participation in the study. The primary variable is the time to first event included in the primary composite endpoint. The primary analysis will be based on the intention to treat (ITT) principle using the FAS, including events occurring on or prior to the primary analysis censoring date (PACD), confirmed by adjudication.

In the analysis of the primary composite endpoint, treatments (dapagliflozin versus placebo) will be compared using a Cox proportional hazards model with a factor for treatment group, stratified by type 2 diabetes (T2D) status at randomisation. The p-value, hazard ratio and 95% confidence interval will be reported.

[figure not shown]
Interim analysis is planned to be performed including approximately 67% of target number of adjudicated primary endpoints.

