9.4.3 Methods for multiplicity control

A closed testing procedure including a pre-specified hierarchical ordering of the primary and secondary endpoints will be utilised. The Type I error will be controlled at an overall two-sided 5% level for multiplicity across primary and secondary endpoints and in consideration of the planned interim analysis. With one interim analysis at 67% of events (see Section 9.5) the two-sided significance level in final analysis, α , will be 4.980%. Statistical significance will be assessed in two branches in a pre-specified order of the endpoints and populations which is further described in the SAP. The significance level α , will be split for the two primary analyses, denoted α_1 and α_2 . If either of the tests of the primary endpoint in the full study population and for LVEF <60% subpopulation is significant at respective levels α_1 and α_2 , the next hypothesis in the respective branch sequence will be tested at the same significance level. The exact split of alpha will be documented in an updated SAP before the interim analysis. If all hypotheses in one arm are rejected, the alpha will be recycled to the other branch.

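### Do the illustrated levels of 1.5% and 2.4%, which sum to 3.9% rather than 4.980%, make the stated powers wrong or leave alpha unspent?

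*Protocol*

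**What the plan says.** Section 9.2 explains that adding the LVEF <60% subpopulation as a second primary test led to a larger event target: "The target number of patients with a primary endpoint has been increased to 1117 in order to provide adequate statistical power for each test". It gives the expected share of events in the subpopulation: "It is anticipated that at least 70% of the events (i.e., approximately 780 events) will be available for the LVEF <60% subpopulation". It then works one example, opening with "To illustrate, assuming a true HR of 0.80, a two-sided alpha of 2.4% allocated to the LVEF <60% subpopulation". In full, the claim for that test is "a two-sided alpha of 2.4% allocated to the LVEF <60% subpopulation will result in a power of 80% to detect a treatment difference". For the other test, "an alpha allocation of 1.5% to the full population will result in 90% power". The synopsis gives the same pair, also as an illustration: "a two-sided alpha of 1.5% would yield a power of 90% for the full population".

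Section 9.4.3 sets the two-sided level for the final analysis at 4.980%, after one interim look, and says that this level "will be split for the two primary analyses". It names the two parts only as α1 and α2 and puts no number on either. The synopsis and sections 9.2 and 9.4.3 all state that the actual split will be fixed in the SAP before the interim analysis.

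**The concern.** The pair 1.5% and 2.4% is the only numerical split in the protocol, and it stands directly behind the target of 1117 events. A reader who comes to it from section 9.4.3 expects the two levels to add up to 4.980%. They add up to 3.9%. A Bonferroni split would use the whole 4.980%. A split that exploits the nesting of the two populations could have nominal levels summing to more than that. The pair fits neither.

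If the levels were the operative ones, 1.08 points of alpha would go unused. The weaker test, in the subpopulation, would run at 80% power when more could be had without another patient or event. The stated powers would then not describe the procedure in section 9.4.3, and the event target might look larger than it need be.

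**Working it through.** **Inputs.** From section 9.2: hazard ratio 0.80, 1117 events in the full population, about 780 (at least 70%) in the subpopulation, two-sided levels 1.5% and 2.4%, 1:1 allocation ("This is based on an overall 1:1 allocation between dapagliflozin and placebo"). From section 9.4.3: 4.980% for the final analysis.

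**1. The stated powers.** With 1:1 allocation, Schoenfeld's approximation is power = Φ(|ln HR|·√d/2 − z), where d is the number of events, z is the normal quantile for half the two-sided level, and |ln 0.80| = 0.2231.

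- Full population: 0.2231 × √1117 / 2 = 3.729. Minus 2.432 (1.5%) this is 1.297, so power is 90.3%. Stated: 90%.
- Subpopulation: 0.2231 × √780 / 2 = 3.116. Minus 2.257 (2.4%) this is 0.859, so power is 80.5%. Stated: 80%.

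In reverse, 90% power at 1.5% needs 1109 events by Schoenfeld or 1118 by Freedman, and 80% at 2.4% needs 772 or 778. The illustration agrees with the event counts.

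**2. The sum.** 1.5% + 2.4% = 3.9%, and 4.980% − 3.9% = 1.08 points. The pair fits inside the available level.

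**3. Familywise error of the pair.** The subpopulation is nested in the full population. At a 70% event share the two test statistics have correlation √0.70 = 0.837. Then 1 − P(|Z1| < 2.432 and |Z2| < 2.257) is about 3.1%, below 4.980%.

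**4. What the remaining 1.08 points could add.**

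| Split (full / subpopulation) | Power, full | Power, subpopulation |
|---|---|---|
| 1.5% / 2.4% (illustration) | 90.3% | 80.5% |
| 1.5% / 3.48% | 90.3% | 84.3% |
| 2.58% / 2.4% | 93.3% | 80.5% |
| 2.49% / 2.49% | 93.1% | 80.9% |

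Each of these exhaustive splits meets or exceeds the stated 90% and 80%. The illustration therefore shows that both targets can be reached within 4.980% with something to spare.

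**5. Could the event target be cut?** At 2.58%, the full-population test alone reaches 90% with about 990 events, which is 1117 − 990 = 127 fewer. But 70% of 990 is 693 subpopulation events. At the 2.4% then left, 0.2231 × √693 / 2 − 2.257 = 0.68, a power of about 75%. To keep 80% at 2.4%, the subpopulation needs about 771 events, or 771 / 0.70 ≈ 1101 in total. Under that split 1117 is close to what is needed.

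**The case for a change.** The strongest case for the concern is that the pair is more than decoration. The text raises the target from 844 to 1117 to power both tests and then offers only these two levels in support. Freedman's formula gives 1117.3 events for 1.5% and 90%, so the 1.5% level looks like the actual basis for the target. The protocol does not say why it leaves 1.08 points aside. A split chosen to use all of 4.980%, about 2.0% and 2.97%, would reach 90% and 80% together with roughly 1045 events, about 70 fewer.

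That much is fair as a remark on presentation. It does not show an error. Each power is tied to its own named level, and the text nowhere says that the two levels exhaust alpha or that 90% and 80% are the operating characteristics of the whole procedure. A target about 70 events above the smallest workable number is a margin: it protects the subpopulation test if its share of events falls short of 70%, and it buys power if the SAP spends the remainder. The loss described would arise only if the SAP adopted the illustrated levels unchanged, and the protocol does not require that.

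A correlation-based split promises more: about 4.5% for the subpopulation beside 1.5% (power about 87%), or about 3.9% for the full population beside 2.4% (about 95%). But section 9.4.3 passes each branch's level on to the secondary hypotheses below it. Levels calibrated to the correlation of the two primary tests are not shown to keep strong control there, because the correlation between secondary tests across branches need not be the same.

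**Conclusion.** The concern does not hold. The sum of 3.9% is right, but no stated figure is wrong, and nothing in section 9.2 or the synopsis contradicts section 9.4.3. The whole 4.980% remains available for the SAP to divide. Provided each test keeps at least its illustrated level, adding the 1.08 points can only raise power, by about 4 points for the subpopulation (80.5% to 84.3%) or 3 for the full population (90.3% to 93.3%). A SAP split that gave one test less than its illustrated level would lower that test's power, but the protocol fixes no such split.

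This rests on a true hazard ratio of 0.80 in both populations, 1117 events, a 70% share in the subpopulation, and the normal approximation for the log hazard ratio. One sentence saying that the illustrated levels are sufficient for the target powers and need not exhaust 4.980% would help readers. It is optional and alters no test, error rate or conclusion.

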9.3 Populations for analyses

For purposes of analysis, the following populations are defined:

Table 5 Population for analysis

Population	Description
Enrolled	All patients who sign the ICF
Full Analysis Set (FAS)	All patients who have been randomised to study treatment, irrespective of their protocol adherence and continued participation in the study. Patients will be analysed according to their randomised investigational product assignment, irrespective of the treatment actually received. The FAS will be considered the primary analysis set for the intention to treat analysis of primary and secondary variables. A subset of the full analysis set consisting of patients with baseline LVEF of <60% (or LVEF <60% subpopulation) will be analysed separately as part of the confirmatory statistical testing procedure.
Safety analysis set	All patients randomly assigned to Study treatment and who take at least 1 dose of investigational product. Patients will be analysed according to the treatment actually received. The Safety analysis set will be considered the primary analysis set for all safety variables

9.4 Statistical analyses

All personnel involved with the analysis of the study will remain blinded until database lock and Clinical Study Protocol deviations identified.

Analyses will be performed by AstraZeneca or its representatives.

A comprehensive statistical analysis plan (SAP) will be developed prior to first patient randomised and any subsequent amendments will be documented, with final amendments finalised before database lock. This section is a summary of the planned statistical analyses of the primary and secondary endpoints. Any deviations from this plan will be reported in the clinical study report.

9.4.1 Efficacy analyses

9.4.1.1 Analysis of the primary variable

The primary variable is the time from randomisation to first event included in the primary composite endpoint. Two hypotheses will be tested simultaneously (i.e., dual primary endpoint analyses): (1) in the full population and (2) in an LVEF <60% subpopulation, with alpha allocated to each test. The primary analysis will be based on the ITT principle using the FAS, including events occurring on or prior to the PACD, adjudicated by the CEA committee.

In the analysis of the primary composite endpoint, treatments (dapagliflozin versus placebo) will be compared using a Cox proportional hazards model with a factor for treatment group, stratified by T2D status at randomisation. The p-value, HR and 95% confidence interval will be reported.

The contribution of each component of the primary composite endpoint to the overall treatment effect will be examined. Methods similar to those described for the primary analysis will be used to separately analyse the time from randomisation to the first occurrence of each component of the primary composite endpoint. HR and 95% confidence intervals will be reported.

Kaplan-Meier estimates of the cumulative incidence to the first occurrence of any event in the primary endpoint will be calculated and plotted, for overall analysis and for the individual components.

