8.1 Enrolment Period

8.1.1 Visit 1, Enrolment (Day -21 to Day -1)

Enrolment of hospitalized patients is allowed.

At enrolment the following assessments and procedures will be completed:

- The patient signs the ICF
 - Patients who agree to the optional sampling of blood for genetic research will provide their consent
- The investigator assesses patient's eligibility criteria and reviews concomitant medications, relevant medications will be recorded in the eCRF

- The patient will be enrolled and assigned an E-code in IxRS assuming inclusion/exclusion criteria are met
 - Demography and relevant medical history (including prior cardiac imaging assessments) will be recorded
 - A physical examination will be conducted
 - NYHA Functional Classification will be evaluated and recorded
 - 12-lead ECG will be recorded
 - Vital signs (BP, pulse), height and weight will be assessed and recorded
- Blood samples will be taken for NT-proBNP, creatinine (for calculation of eGFR) and HbA1c assessment (central laboratory)

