8.2 Treatment period

8.2.1 Visit 2, Randomisation (Day 1)

Prior to Visit 2, the investigator will assess eligibility based on the central laboratory assessments from Visit 1. Patients not eligible will be considered screen failures and should not continue to Visit 2.

Randomisation of hospitalized patients is allowed.

At randomisation, the following assessments and procedures will be completed:

- Medical history (including cardiac imaging assessments) will be re-assessed
- A physical examination will be conducted
- A pregnancy test for women of child-bearing potential will be done locally with a dipstick provided by central laboratory with result recorded in the medical record
- Vital signs (BP, pulse) will be assessed and recorded
- NYHA Functional Classification will be evaluated and recorded
- The investigator will re-assess the inclusion and exclusion criteria
- KCCQ, PGIS and EQ-5D-5L questionnaires will be completed
- Review of concomitant medication and recording of relevant medications
- If the patient has experienced any SAEs since last visit, this will be recorded in the eCRF

- Randomisation 1:1 ratio to IP (either dapagliflozin at 10 mg or placebo) will be done in IxRS
- IP will be dispensed via IxRS to the patient. The patient will be instructed to take the IP in accordance with protocol without interruptions, and to bring all dispensed bottles to all study visits
- Patients who have consented to sampling for genetic research, will provide a blood sample

8.2.2 Visit 3 (Day 30; ±7 days):

At Visit 3, the following assessments and procedures will be conducted:

- KCCQ and PGIS questionnaires will be completed
- NYHA Functional Classification will be evaluated and recorded
- Vital signs (BP, pulse) will be assessed and recorded
- Review and updating of concomitant medication and recording of relevant medications
- Review and recording of any cardiac and HF related procedures
- Review of potential efficacy and safety events including COVID-19 testing results
- If the patient has experienced any potential endpoints, SAEs, DAEs and/or amputations, adverse events (AEs) leading to amputation and potential risk factor AEs for amputations affecting lower limbs since the last visit, this will be recorded in the eCRF
- Blood samples will be taken for creatinine (for calculation of eGFR) assessment (central laboratory)

8.2.3 Visit 4 (Day 120 ±7 days):

At Visit 4, the following assessments and procedures will be conducted:

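### The primary Cox model is valid but omits baseline NT-proBNP, which the protocol uses in planning event rates and measures before randomisation, so both dual primary tests give up a little power

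*Protocol*

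**What the plan says.** Section 9.4.1.1 fixes the primary comparison: the arms are "compared using a Cox proportional hazards model with a factor for treatment group, stratified by T2D status at randomisation". The statistical methods part of the synopsis (section 1.2) repeats this: "compared using a Cox proportional hazards model with a factor for treatment group, stratified by type 2 diabetes (T2D) status at randomisation". The same model serves both dual primary tests. T2D status is the only randomisation stratum (section 6.3.1.1).

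Section 9.2 takes its event-rate assumptions from sub-analyses of two earlier HFpEF trials "by geographic region, NT-proBNP levels, prior hospitalisation for HF, and T2D status". It also ties the 9% annual placebo rate to the NT-proBNP entry threshold of 300 pg/ml.

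NT-proBNP is drawn for the central laboratory at Visit 1 (section 8.1.1) and is inclusion criterion 5 (section 5.1). Before Visit 2, "the investigator will assess eligibility based on the central laboratory assessments from Visit 1" (section 8.2.1).

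The protocol leaves the sensitivity analyses (9.4.1.4), the list of subgroup variables (9.4.1.3) and the alpha split (9.2, 9.4.3) to the SAP. It does not leave the covariates of the primary model open.

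**The concern.** A Cox model that omits a prognostic baseline variable remains valid under the null. When treatment works, however, it estimates a log hazard ratio closer to zero than the one that holds at a given level of that variable. The standard error hardly changes, so power falls.

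Here the omitted variable is one that the sponsor's own planning treats as related to event rate. It is measured before randomisation in a central laboratory and should be almost complete, because eligibility depends on it.

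The current protocol raised the event target from 844 to 1117 to give each of the two tests adequate power. A covariate already in the database buys some of the same thing without patients or events. The LVEF <60% test has the lower power in the protocol's illustration (80% against 90%) and gains slightly more.

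**Working it through.** **Inputs from section 9.2.** HR 0.80; 1:1 allocation; 1117 events at two-sided alpha 1.5% (full population); about 780 events at two-sided alpha 2.4% (LVEF <60%); 9% per year placebo rate; 11% subacute patients at 24% in year 1; 6100 patients; 26 months of recruitment.

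**Assumptions not in the protocol.** The standard deviation (SD) of the NT-proBNP risk score on the log-hazard scale among randomised patients is 0.3, 0.5 or 0.7. This equals a hazard ratio per SD of exp(0.3) = 1.35, exp(0.5) = 1.65 or exp(0.7) = 2.01. The T2D share is 45%. The LVEF <60% group is a random 70% of patients.

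**Step 1: reproduce the stated power (Schoenfeld).** Expected z = √(events/4) × ln(1/0.80); power = Φ(z − critical value).
- Full: 16.711 × 0.2231 = 3.729; 3.729 − 2.432 = 1.297; power 90.3% (stated 90%).
- LVEF <60%: 13.964 × 0.2231 = 3.116; 3.116 − 2.257 = 0.859; power 80.5% (stated 80%).

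The planned model meets its targets if 0.80 is the hazard ratio under that model.

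**Step 2: simulate with and without the covariate.** Event-driven trials were stopped at event 1117, with 4000 replicates per setting. The T2D-stratified Cox model was fitted to the same data both ways, and power was taken as Φ(mean z − critical value).

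| SD of score | z ratio, adjusted/unadjusted | Unadjusted log HR as share of conditional |
|---|---|---|
| 0.3 | 1.008 | 0.992 |
| 0.5 | 1.025 | 0.975 |
| 0.7 | 1.053 | 0.949 |

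A separate simulation with 1200 replicates per setting gave similar ratios: about 1.007 at a hazard ratio of 1.3 per SD, 1.015 to 1.019 at 1.5, 1.03 at 1.7 and 1.05 at 2.0. With no prognostic effect the ratio was 1.000, so adjustment cost nothing. A third run with 500 replicates in the full population gave 1.011, 1.029 and 1.053 at SD 0.3, 0.5 and 0.7.

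**Step 3: convert to power.** The result depends on what HR 0.80 refers to.

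| Reading of HR 0.80 | Population | Unadjusted, SD 0.3 / 0.5 / 0.7 | Adjusted |
|---|---|---|---|
| HR under the planned model | Full | about 89% throughout | 90.0 / 91.0 / 92.5% |
| HR under the planned model | LVEF <60% | about 79% throughout | 79.9 / 81.2 / 83.3% |
| HR conditional on NT-proBNP | Full | 89.0 / 87.7 / 85.6% | about 89.5% |
| HR conditional on NT-proBNP | LVEF <60% | 78.5 / 76.7 / 74.2% | about 79% |

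Simulated unadjusted power is about 1 point below the Schoenfeld figure, so the comparison to read is the difference between the two models. As a cross-check, the ratios can be applied to the Schoenfeld z. Full: 3.729 × 1.008, 1.025, 1.053 = 3.759, 3.822, 3.927, giving 90.8, 91.8 and 93.2%. LVEF <60%: 3.116 × the same ratios = 3.141, 3.194, 3.281, giving 81.2, 82.6 and 84.7%.

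**Step 4: express it in events.** The squared ratios are 1.016, 1.051 and 1.109, equivalent to about 18, 57 and 122 extra events on top of 1117.

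**Step 5: check type I error (SD 0.7, no treatment effect).** At nominal 1.5%, rejection was 1.70% unadjusted and 1.78% adjusted (Monte Carlo SE 0.19). At nominal 2.4% it was 2.80% and 2.68% (SE 0.24). All lie within two standard errors of nominal.

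**Step 6: vary the shape.** With a right-skewed score (a normal cut at −0.5 SD and rescaled to the same SD; 2000 replicates), the ratio was 1.012 at SD 0.3 and 1.084 at SD 0.7. The gain was then about 1 to 6 points (full) and 1 to 7.5 points (LVEF <60%).

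**Step 7: check subacute status.** As a stratum on its own it adds only 0.3% to 0.4% to z, under 0.5 point of power.

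**The case against.** The strongest reply is that nothing is wrong. The model follows the randomisation and the stated powers reproduce without adjustment. On that view, preferring a slightly more powerful model is a matter of taste. It stands that this is no error, and the point is graded accordingly.

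Second, the protocol gives no risk gradient for NT-proBNP above the entry threshold, and it lists region and prior HF hospitalisation alongside it without quantifying those either. This is fair. The size rests wholly on the assumed range, and at its lower end the gain is under 1 point. NT-proBNP is singled out because it is a central-laboratory value, needed for eligibility, and tied by section 9.2 to the 9% placebo rate. It is not singled out because the protocol measures its effect.

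Third, the entry threshold could narrow the spread of NT-proBNP. A normal score cut at −0.5 SD keeps only about 0.70 of its SD, so 0.7 would become about 0.49. The 6 and 7.5 point figures apply only if the SD among randomised patients is still 0.7 after that cut, and they should be read as an outer bound.

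Fourth, the protocol does not say that HR 0.80 is conditional on NT-proBNP. If it is the hazard ratio under the planned model, no stated power is lost and adjustment is pure gain. Finally, the threshold differs with atrial fibrillation or flutter (600 against 300 pg/ml), so a single term may be somewhat weaker than modelled. None of these points reverses the direction.

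**Conclusion.** The concern holds as a small, avoidable loss of efficiency in a valid analysis. Over an assumed SD of 0.3 to 0.7 on the log-hazard scale, adjusting for NT-proBNP gains about 0.5 to 4 points of power in the full population and about 0.7 to 5 points in LVEF <60%. The direction does not depend on the assumed strength, provided NT-proBNP is prognostic at all, but the size does. The figures use the protocol's illustrative alphas of 1.5% and 2.4% and will move with the final split. Subacute status, the only risk driver that the protocol quantifies, adds almost nothing and is not part of the claim. The change is desirable but not necessary; confidence is medium.

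**What to change.** Before the interim analysis, and without access to treatment codes:

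- Pre-specify log(NT-proBNP) at Visit 1 as a covariate in the T2D-stratified Cox model for the primary endpoint, in both populations and at the interim.
- State that the resulting hazard ratio is conditional on NT-proBNP.
- Replace any missing Visit 1 value with the overall median, regardless of arm, so that every patient in the full analysis set is kept.
- Keep the T2D-stratified model without the covariate as a supplementary analysis.
- Say whether the components, CV death and all-cause mortality follow the adjusted model, since sections 9.4.1.1 and 9.4.1.2 analyse them in a similar way to the primary endpoint.

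Subacute status is optional. If it is used, make it a stratum and not a fixed covariate, because section 9.2 assumes its excess hazard ends after the first year.

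The cost is protocol and SAP wording, with no new data. The real price is a change of estimand, from the hazard ratio of the current model to one conditional on NT-proBNP. That is why the current model should still be reported beside it.
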